## SYNOPSIS

**Sponsor:** Transgene

**IMP:** TG4050, an MVA based, mutanome-targeted individualized immunotherapy

**Study Title**

A phase I trial evaluating a mutanome-directed immunotherapy in patients with high grade serous carcinoma (HGSC) of the ovary, fallopian tube or peritoneum who experience an asymptomatic relapse

**Study N°:TG4050.01**

**EudraCT N°: 2018-003266-14**

**Coordinating / Principal Investigator:** [name], Mayo Clinic, Rochester, USA

**Investigational Centers/Countries:** USA (3 sites from Mayo Clinic) and France (3 sites)

**Study Period:** Q4 2019-Q4 2024

**Clinical Phase:** I

**Objectives**

Primary objective: to evaluate the safety and tolerability of multiple subcutaneous (SC) injections of a neoantigen-directed active immunotherapy (TG4050) in ovarian, fallopian or peritoneal HGSC patients with an asymptomatic relapse.

Secondary objectives: to evaluate:

- Failure to provide TG4050
- Failure to treat with TG4050
- CA-125 doubling time and half-life as appropriate, time to normalization and response according to Gynecological Cancer InterGroup (GCIG) criteria
- Time to measurable relapse in Cohort A and Time to progression in Cohort B per RECIST 1.1
- Tumor response by using RECIST 1.1

Translational research endpoints:

CCI

**Methodology**

This is a multicenter, open-label, single arm phase I study evaluating TG4050, an individualized active immunotherapy which refers to a mutanome-directed immunotherapy based on a Modified Vaccinia virus Ankara (MVA) vaccine specifically designed to target tumor-specific antigens identified in each ovarian, fallopian or peritoneal HGSC patient with an asymptomatic relapse.

The study will consist of 2 parts for each patient:

- A screening period starting at least 6 months after completion of standard first-line treatment including a platinum-based chemotherapy in patients with high risk serous fallopian, peritoneal or ovarian cancer who underwent cytoreductive surgery and achieved clinical complete response after platinum-based chemotherapy as demonstrated by non-evidence of disease on the last CT-scan and normal CA-125. High risk is defined by high grade and stage IIIC or stage IV disease. For each of those patients, an individualized, mutanome-directed immunotherapy TG4050 will be assembled.

**Sponsor:** Transgene**IMP:** TG4050, an MVA based, mutanome-targeted individualized immunotherapy

- A treatment period with TG4050 monotherapy starting in:
  - o Cohort A: when patients develop an asymptomatic relapse defined on the basis of progressive serial elevations of serum CA-125 (GCIG criteria) or documentation of low volume radiological disease with CA-125 > Upper Limit of Normal (ULN). Low volume radiological disease is defined as radiologically visible disease excluding intra-hepatic or intra-splenic metastases, ascites or pleural effusion thought to require drainage
  - o Cohort B: when patients develop an asymptomatic relapse with measurable disease excluding intra-hepatic or intra-splenic metastases, ascites or pleural effusion thought to require drainage, whatever serum CA-125 level and for whom further treatment is not planned within 2 months. Longest diameter on CT-scan must not exceed 2 cm for non-nodal lesions and 2.5 cm in short axis for nodal lesions

Patients will receive TG4050 up to a total of 20 injections or until disease progression justifying initiation of further treatment, unacceptable toxicity including occurrence of a dose-limiting toxicity, or patient withdrawal for any reason, whichever occurs first.

A safety run-in phase will be conducted in the first 3 treated patients from Cohort A or B who will be observed during the 6 weeks after the first administration of TG4050. During this phase, each patient will be monitored for 4 weeks after the first injection of TG4050 before the next patient can be enrolled.

Enrolment of the next patients will be allowed if none of the 3 patients has experienced during the six weeks run-in phase:

- any grade  $\geq 3$  toxicity that is at least possibly related to TG4050, with the following exception: pre-existing grade 2 fatigue at baseline that would worsen up to grade 3
- any death

The occurrence of any of those events will trigger a study hold. An evaluation of the cause of toxicity will be performed and corrective measures, if appropriate, will be proposed before recruitment in the study can be reinitiated.

[figure not shown]
Beyond the safety run-in phase, a dose-limiting toxicity is defined as any treatment-emergent AE  $\geq 3$  toxicity that is at least possibly related to TG4050, with the following exceptions: pre-existing grade 2 fatigue at baseline that would worsen up to grade 3.

In any case, patients experiencing a dose-limiting toxicity will discontinue study treatment permanently.

An Independent Data Monitoring Committee (IDMC) will be set up for the purpose of reviewing patients' safety data and the conduct of the study.

The IDMC will meet at completion of the safety run-in phase to analyze and review the safety data of the first 3 patients from Cohort A or B. The IDMC will then recommend whether it is possible to pursue patient enrolment as per study protocol. In addition to the review of the first 3 patients, the IDMC will review safety data of all patients included every 3 months during the first year and every 6 months thereafter.

*Ad hoc* meetings may be held upon necessity.

**Sponsor:** Transgene**IMP:** TG4050, an MVA based, mutanome-targeted individualized immunotherapy**Graphical synopsis****Number of Patients**

- Screening period: an approximate number of 60 patients will participate.
- Treatment period:
  - o Cohort A: at least 13 patients will be enrolled to allow sufficient number of patients evaluable for safety, efficacy and immunological analyses.
  - o Cohort B: Number of patients included at the time of full accrual in Cohort A with a maximum of 10 patients.

**Inclusion criteria**Screening period

- 1- Signed written informed consent in accordance to ICH-GCP and national/local regulation before any protocol-related procedures that are not part of normal patient care.
- 2- Female patients  $\geq 18$  years of age
- 3- Histologically confirmed high grade, stage IIIC or stage IV (FIGO staging) serous ovarian, fallopian or primary peritoneal carcinoma with abnormal CA-125 at diagnosis
- 4- Patients who have undergone primary debulking surgery or interval debulking surgery and completed a total of at least 5 cycles of taxane-platinum combination. Note: patients may have received concurrent or maintenance bevacizumab or a PARP inhibitor.
- 5- Patients must have achieved a complete response to therapy, as demonstrated by no residual disease on most recent CT scan and normal CA-125.
- 6- Patient who remains disease free at least 6 months from last prior dose of cytotoxic chemotherapy (maintenance therapy with bevacizumab or a PARP inhibitor is allowed).
- 7- Available tumor tissue, banked from previous abdominal debulking surgery and/or from a core needle biopsy performed at diagnosis if the patient received neoadjuvant chemotherapy, and peripheral blood samples for exome and transcriptome sequencing.

Treatment period

- 8- Eastern Cooperative Oncology Group (ECOG) performance status of 0 or 1 at treatment period initiation
- 9- Patients who have developed an asymptomatic relapse as defined by
  - o Cohort A: CA-125  $\geq 2$  times ULN on 2 occasions at least 1 week apart (GCIG criteria) or low volume radiological disease and CA-125  $>$  ULN. Low volume radiological disease is defined as radiologically visible disease excluding intra-hepatic or splenic metastases, ascites or pleural effusion thought to require drainage.
  - o Cohort B: patient asymptomatic with measurable disease, excluding intra-hepatic or splenic metastases, ascites or pleural effusion thought to require drainage, whatever serum CA-125 level and for whom further treatment is not planned within 2 months. Longest diameter on CT-scan must not exceed 2 cm for non-nodal lesions and 2.5 cm in short axis for nodal lesions.

**Sponsor:** Transgene**IMP:** TG4050, an MVA based, mutanome-targeted individualized immunotherapy

10- Adequate hematological, hepatic and renal functions:

- Hemoglobin  $\geq 9.0$  g/dL
- Neutrophils count  $\geq 1.5 \times 10^9/L$
- Lymphocytes count  $\geq 0.9 \times 10^9/L$
- Platelets count  $\geq 100 \times 10^9/L$
- Total bilirubin  $\leq 1.5 \times$  ULN (except for patients with Gilbert's syndrome)
- Aspartate aminotransferase (AST)  $\leq 2.5 \times$  ULN
- Calculated creatinine clearance  $\geq 45$  mL/min using the Cockroft & Gault formula or  $\geq 45$  mL/min/1.73m^2 using other methods

11- Patients who received standard maintenance therapy will stop before initiation of TG4050 administration. A free-interval of at least 30 days will be respected before first dosing of TG4050 except for PARP inhibitor (at least 14 days).

**Exclusion criteria****Screening period**

- 1- Patient having received any cancer immunotherapy including cancer vaccines, any antibody/drug targeting T cell co-regulatory proteins such as anti-PD1, anti-PDL1 or anti-CTLA-4
- 2- Patients with other active malignancy  $\leq 3$  years prior to registration except non-melanoma skin cancer, stage 0 in situ carcinoma and recent early stage papillary thyroid cancer. If there is an history of prior malignancy, patient must not be receiving other specific treatment for their cancer
- 3- Patient post-organ transplantation, including allogeneic stem cell or bone marrow transplantation. History of blood transfusion within 3 weeks prior to study entry visit.
- 4- Known history of positive testing for Human Immunodeficiency Virus (HIV) or known AIDS (Acquired Immune Deficiency Syndrome)
- 5- Any known allergy or reaction to eggs or attributed to compounds of similar chemical or biological composition to therapeutic vaccines/immunotherapeutic products
- 6- Positive serology for Hepatitis C Virus (HCV) or positive serum Hepatitis B surface antigen (HBsAg) within 3 months prior to or at study entry (tests required)

**Treatment period**

- 7- Measurable disease associated with the appearance of symptoms justifying initiation of further treatment.
- 8- Major surgery within 4 weeks prior to treatment start
- 9- Treatment with another investigational agent within 30 days prior to TG4050 treatment initiation.
- 10- Patients under chronic treatment with systemic corticosteroids or other immunosuppressive drugs for a period of at least 4 weeks and whose treatment was not stopped 2 weeks prior to TG4050 treatment initiation planned date, with the exception of patients with adrenal insufficiency who may continue corticosteroids at physiological replacement dose, equivalent to  $\leq 10$  mg prednisone daily. Steroids with no or minimal systemic effect (topical, inhalation) are allowed.
- 11- Vaccination for the prevention of infectious diseases with a live vaccine during the four-week period prior to TG4050 treatment initiation planned date. Furthermore, patients should not receive any live vaccine during the period of study treatment administration.
- 12- Patient with any underlying medical condition, that in the opinion of the investigator, could make the patient inappropriate for entry into this study or interfere significantly with the proper assessment of safety or toxicity of the study treatment.
- 13- Uncontrolled intercurrent illness including, but not limited to ongoing or active infection, symptomatic congestive heart failure, unstable angina pectoris, cardiac arrhythmia or psychiatric illness/social circumstances that could limit compliance with study requirements.
- 14- History of myocardial infarction  $\leq 6$  months.

**Sponsor:** Transgene**IMP:** TG4050, an MVA based, mutanome-targeted individualized immunotherapy**IMP: Dose, Mode of Administration**In this study, the Investigational Medicinal Product (IMP) is TG4050.

- The IMP is an individualized MVA construct, mutanome-directed immunotherapy tailored to each patient and derived from a replication deficient strain of vaccinia virus (Modified Vaccinia virus Ankara, MVA).
- The individualized TG4050 construct will be assembled for each patient during the screening period. Study treatment will be started when a patient develops an asymptomatic relapse.
- Patients will receive subcutaneous (SC) injections of TG4050 at a dose of  $1 \times 10^8$  PFU weekly for the first 6 weeks and then every 3 weeks up to a total of 20 injections unless disease progression justifying initiation of further treatment, unacceptable toxicity including occurrence of a dose-limiting toxicity, or patient withdrawal for any reason, whichever occurs first.

**Reference / Associated Therapy**

Permitted medicines and therapies:

- Any medications that are considered necessary for the patients' welfare and will not interfere with the trial medication may be given at investigator's discretion.
- The use of the following drugs will not be restricted during the course of the study: G-CSF, erythropoietin, antiemetics and analgesics.
- Topical, ocular, intra-articular, intranasal and inhalational corticosteroids (with minimal systemic absorption)
- The use of systemic corticosteroids during the study is restricted as follows: for short term treatment ( $\leq 7$  days) of allergic reactions, or for replacement for adrenal insufficiency at doses equivalent to  $\leq 10$  mg prednisone daily.

Non-permitted medicines and therapies during the study treatment period:

- Immunosuppressive agents
- Immunosuppressive doses of systemic corticosteroids per restrictions described above.
- Any concurrent antineoplastic therapy
- Any live vaccine for the prevention of infectious disease
- Any other investigational agent

**Duration of Study Treatment**

TG4050 will be administered up to a total of 20 injections or until disease progression justifying initiation of further treatment, unacceptable toxicity including occurrence of a dose-limiting toxicity, or patient withdrawal for any reason whichever occurs first.

**Criteria for Evaluation****Failure to provide rate**

The proportion of patients for whom TG4050 cannot be provided and the reason for not being able to provide the vaccine will be recorded.

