### 9.3.2. Secondary endpoints

- Failure to provide rate: percentage of patients for whom TG4050 cannot be provided and the reason for not being able to provide the vaccine will be recorded.
- Failure to treat rate: percentage of patients who cannot receive TG4050 and the reason that prevent patient from being treated.
- CA-125 doubling time and half-life as appropriate
- Time to normalization of CA-125
- Response according to GCIC criteria
- Time to measurable relapse in Cohort A and Time to progression in Cohort B per RECIST 1.1
- Tumor response according to RECIST 1.1

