### 3.2 Secondary objectives

Secondary endpoints are to evaluate the rate of failure to provide TG4050 and failure to treat with TG4050, to evaluate, if applicable, the CA-125 doubling time/time to normalization (this analysis won't be performed given the low number of evaluable patients ) and response according to GCIG criteria and time SAP-template version of 4 Jan 2024

to measurable relapse in cohort A and time to progression in cohort B per RECIST 1.1 and the tumor response according to RECIST 1.1.

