### **8.2 Patient enrollment and disposition**

#### **8.2.1 Screening status**

The number of patients screened (i.e., who signed informed consent) will be displayed. All patients who failed to meet eligibility criteria after ICF signature will be considered as screening failure and reported in the study report. The number of these patients and the primary reason for non-inclusion will be also displayed. Percentages will be calculated over the number of patients screened.

A listing will be performed to present all screen failures with the reason(s) of non-inclusion for each part (screening period and treatment period). The number of screening failure patients and reasons for screening failure and reasons will be summarized.

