### **8.7 Analysis of patients not treated**

In case of TG4050 individualized product unavailability in due time or TG4050 manufactured product not administered for any reason, the reason will be documented as a Failure to provide or a Failure to treat and the patient will be withdrawn from the study. The patient will continue to benefit from routine medical monitoring and will receive SOC in case of recurrence as per normal practice.

- **Failure to treat**

Patients who cannot receive TG4050 at the time of planned treatment will be listed. The reason that prevents a patient from being treated will be recorded. Reasons can be Inclusion/exclusion criteria for treatment period not met, lost to follow-up, ICF withdrawn, Adverse Event or Failure to provide. The reason of failure to treat will be listed by type (SCOS report and eCRF page “End of study”).

- **Failure to provide**

Patients for whom TG4050 cannot be provided according to the SCOS report will be listed. Reasons for not being able to provide the vaccine will also be recorded. Reasons for failure to provide can be any issue at any step of TG4050 production. The reason of failure to provide will be listed by type (SCOS report and eCRF page “End of study”).

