### 10.2 Listings

Listing number	Title
16.2	PATIENS DATA LISTINGS
16.2.1	Discontinued patients
Listing 16.2.1.1	Screen failure patients and non-inclusion reasons – SCR
Listing 16.2.1.2	Patients' disposition – SAF
16.2.2	Protocol deviation for enrolled patients
Listing 16.2.2.1	Protocol deviations at inclusion for treated patients – SAF
Listing 16.2.2.2	Protocol deviations during study for treated patients – SAF
16.2.4	Demographic data and Baseline characteristics by patient (enrolled patients)
Listing 16.2.4.1.1:2	Demographic and baseline characteristics: SCR/SAF
Listing 16.2.4.2.1:2	History of studied disease – SCR/SAF
Listing 16.2.4.3. 1:2	Prior Anti-Cancer Therapy: Medication – SCR/SAF
Listing 16.2.4.4.1	Relevant Medical History and current Medical Conditions – SAF
Listing 16.2.4.5.1:2	CA-125 concentration at study entry and during screening period – SCR/SAF
Listing 16.2.4.6	Signs and symptoms at baseline – SAF
Listing 16.2.4.7	Serology – SCR/SAF
16.2.5	Compliance and study conduct data
Listing 16.2.5.1	TG4050 administration – SAF
Listing 16.2.5.2	TG4050 administration per patient – SAF
Listing 16.2.5.3	Delayed, cancelled or stopped administration of TG4050 (Listing) – SAF
Listing 16.2.5.4	Discontinuation of study treatment and study (Table) – SAF
Listing 16.2.5.5	Prior and concomitant medications (on or after D1) – SAF
Listing 16.2.5.6	Prior and concomitant medications (before D1) – SAF
Listing 16.2.5.7	Further anti-cancer therapies – SAF
16.2.6	Individual efficacy response data by patient (enrolled patients)
Listing 16.2.6.1	CA-125 concentration during treatment period – SAF
Listing 16.2.6.2	Failure to treat/provide – SCR
Listing 16.2.6.3	Objective tumor assessments by evaluation – SAF
Listing 16.2.6.4	Detailed tumor assessment – SAF
Listing 16.2.6.5	Time to measurable relapse / Time to Progressive Disease – SAF
16.2.7	Adverse event listings by patient
Listing 16.2.7.1	Adverse events – SAF
Listing 16.2.7.2	Adverse events related to TG4050 – SAF
Listing 16.2.7.3	Serious Adverse events before treatment – SAF
16.2.8	Listing of individual laboratory measurements by patient

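### Failure to provide and failure to treat are defined as rates, but the SAP plans only a listing and sets no at-risk denominator for either

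*Protocol*

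**What the plan says.** The protocol treats both endpoints as proportions. The synopsis states: "The proportion of patients for whom TG4050 cannot be provided and the reason for not being able to provide the vaccine will be recorded". Section 9.3.2 repeats this as "Failure to provide rate: percentage of patients for whom TG4050 cannot be provided" and "Failure to treat rate: percentage of patients who cannot receive TG4050". Neither place names a denominator. SAP 3.2 keeps the same quantity: "Secondary endpoints are to evaluate the rate of failure to provide TG4050 and failure to treat with TG4050".

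The analysis text is different. SAP 8.7 says of failure to treat, "Patients who cannot receive TG4050 at the time of planned treatment will be listed", and of failure to provide, "Patients for whom TG4050 cannot be provided according to the SCOS report will be listed". In SAP section 10 the only dedicated output is Listing 16.2.6.2, "Failure to treat/provide", on the screening population. Section 10.1 has no table for either endpoint.

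The documents do foresee a related percentage. Protocol 9.1.1 and SAP 6.1 plan to analyse the share of screened patients who are not treated, with reasons. Protocol 8.1 names failure to provide and failure to treat among those reasons. Table 14.1.1.1 covers screen failures and their reasons, and SAP 8.2.1 gives its base: "Percentages will be calculated over the number of patients screened". Screened means having signed consent (SAP 6.1).

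**The concern.** Someone following the SAP's output list exactly would produce no rate, among patients at risk, for two secondary endpoints that the SAP retains. SAP 3.2 openly drops the CA-125 doubling-time and normalization analysis because few patients are evaluable. It says nothing of the kind about these two rates, so the objective and the analysis simply disagree.

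The fallback percentage has an unsuitable base. Manufacturing is requested for patients who meet the screening-period criteria (Protocol 6.1.2 and 7.1.1). Treatment can start only in patients who relapse without symptoms and have product available (Protocol 5.2 and 6.2). Consented patients outside these groups were never exposed to the failure in question.

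The failure-to-treat numerator is also unsettled:

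- One sentence of SAP 8.7 ties it to the time of planned treatment. Another counts any manufactured product that is not given, whatever the reason, as one failure or the other; Protocol 7.1.1 says the same.
- On the broad wording, patients withdrawn because they had not relapsed 36 months after manufacture (SAP 2.2) can become failures.
- SAP 8.7 lists failure to provide as a reason for failure to treat, so one patient can count in both.
- SAP 8.7 lists loss to follow-up as a failure-to-treat reason, whereas Protocol 8.1 sets it apart.

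Protocol 1.2 describes the trial as one of feasibility and safety. It stopped with 6 treated patients (SAP 4), so whether a personalised product can be made and delivered in time is one of the questions it can still inform.

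**Working it through.** There is no plan figure to reproduce. Neither document gives an expected rate or target precision for these endpoints, and no sample size is calculated (Protocol 9.2, SAP 7.1).

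**Inputs from the documents.** Treated: 6 (SAP 4). Planned for screening: about 60 (Protocol 3.2, SAP 2.2). Interval method: exact Clopper-Pearson 95% (SAP 8.1).

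**Assumed, for illustration only.** 60 consented; 50 manufacturing requests; 5 without a released product; hence 50 − 5 = 45 products. Of these 45 patients, 6 were treated, 4 relapsed without symptoms but were not dosed, and 35 never relapsed (6 + 4 + 35 = 45).

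**Interval.** For x out of n, the lower limit is the 2.5% quantile of Beta(x, n − x + 1) and the upper limit is the 97.5% quantile of Beta(x + 1, n − x).

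**Failure to provide.** Let S be the number consented, R the number with a request, and x the failures, all of which lie within R. Then x/S = (x/R) × (R/S), and R ≤ S, so x/S ≤ x/R whatever the counts.

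- All consented: 5/60 = 8.3% (2.8 to 18.4%).
- With a request, R = 50: 5/50 = 10.0% (3.3 to 21.8%).
- With a request, R = 30: 5/30 = 16.7% (5.6 to 34.7%).

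**Failure to treat.** The same assumed patients give:

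| Reading | Calculation | Result (exact 95% CI) |
|---|---|---|
| At risk: asymptomatic relapse, product available | 4/(6 + 4) | 40.0% (12.2 to 73.8%) |
| Not dosed at planned treatment, over all consented | 4/60 | 6.7% (1.8 to 16.2%) |
| Any product made but not given, over all consented | (4 + 35)/60 | 65.0% (51.6 to 76.9%) |
| Every untreated patient, over all consented | (60 − 6)/60 | 90.0% (79.5 to 96.2%) |

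The second row lies below the at-risk rate; the third and fourth lie above it.

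**Sensitivity.** If 40 or 20 had consented, the second row would be 4/40 = 10.0% or 4/20 = 20.0%, and the last row 34/40 = 85.0% or 14/20 = 70.0%. With 2 or 6 undosed at relapse instead of 4, the at-risk rate is 2/8 = 25.0% (3.2 to 65.1%) or 6/12 = 50.0% (21.1 to 78.9%).

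**Overlap.** If the 5 failures to provide also count as failures to treat, the narrow numerator becomes 4 + 5 = 9, or 9/60 = 15.0%. The two endpoints then hold 5 + 9 = 14 entries for 9 patients.

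**The case against.** A reader might infer that no percentage is planned at all. The documents do not support that: Protocol 8.1 and 9.1.1, SAP 6.1 and 8.2.1, and Table 14.1.1.1 make a percentage by reason foreseeable, and SAP 8.1 allows exact intervals for proportions where appropriate. What is missing is a dedicated estimate and a stated at-risk base.

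A reader might also infer that using all consented patients understates both failure rates. That is secure only for failure to provide. Under the broad wording in SAP 8.7, patients who never relapsed enter the failure-to-treat numerator, and the rate can be inflated instead.

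Further points carry weight:

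- The gap starts in the protocol, which names no denominator and itself uses the consented population for patients not treated. The base in SAP 8.2.1 is written for screening failures and is not expressly assigned to these endpoints. An end-to-end yield among all consented patients is a legitimate quantity and should stay.
- Restricting failure to treat to asymptomatic relapse with product available removes some patients whom the current text may count: those who never relapse, withdraw or are lost beforehand. They must be shown, not dropped.
- This is a descriptive phase I study that stopped early, with no decision rule on these rates. The SAP's document history records that efficacy tables were removed at version 3.0, so relying on listings may be deliberate. Listings 16.2.6.2 and 16.2.9.1 should also let a reader count failures and requests.

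The last point limits the importance but does not remove the conflict. SAP 3.2 retains the rates, and a reader counting from listings would still have to choose the numerator and denominator.

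**Conclusion.** The concern holds in limited form. Two retained secondary endpoints are defined as rates, yet the SAP plans only a listing for them. The one percentage that could appear is over all consented patients. For failure to provide, that percentage can only equal or understate the rate among patients with a manufacturing request; this follows algebraically provided every failure arises after a request. For failure to treat, the direction depends on which sentence of SAP 8.7 defines the numerator: in the illustration the all-consented figure runs from 6.7% to 90.0%, against 40.0% at risk.

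The size is uncertain. Only the 6 treated is observed. Sixty is a planned approximate number in a study stopped for low inclusion, and all other counts are assumed. The point should be fixed before the final analysis. It does not touch the primary safety analysis.

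**What to change.** Add one table to SAP 8.7 and section 10.1, giving n/N and the Clopper-Pearson 95% interval for each endpoint:

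- **Failure to provide:** patients without a released product, divided by patients with a manufacturing request (Listing 16.2.9.1).
- **Failure to treat:** patients not dosed, divided by patients with an asymptomatic relapse and product available.

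Make the numerators mutually exclusive by removing failure to provide from the failure-to-treat reasons. Show on separate lines the patients who never relapsed, those who withdrew or were lost before relapse, and any whose relapse was not asymptomatic. Keep the all-consented percentage, labelled as such, and the listing of reasons alongside.

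The cost is one extra table from information the SAP already draws on: manufacturing requests, the SCOS report and the end-of-study page. The failure-to-treat interval will be wide (4/10 gives 12 to 74%), and the failure-to-provide rate can only stay the same or rise compared with the all-consented figure. No clinical rule changes.
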